11.1. Subject Information

The primary analysis population for the efficacy endpoint will be the intent-to-treat population in the randomized phase of the study. The subjects in the safety run-in cohort will also be included in the efficacy analyses and listed separately. Safety will be evaluated for all subjects who have received at least 1 dose of study drug (atezolizumab or daratumumab). The pharmacokinetic analyses will be performed on the population described in Section 11.4.

11.2. Sample Size Determination

Assuming that the ORR for atezolizumab monotherapy is approximately 20%, and the addition of daratumumab would improve ORR by 20% to 40%, 90 subjects need to be randomized with a 1:1 ratio in order to achieve 80% power to detect this difference with a one-sided alpha of 0.10. In the event that benefit from the combination is not observed across the overall study population, targeted enrollment of subgroups, based on tumor PD-L1 expression level, may be implemented, based on DMC recommendations (see Section 11.3). As such, approximately 50 additional subjects in the TC2/TC3 subgroups may be enrolled to preliminarily evaluate the treatment effect. If the ORR is 25% for atezolizumab monotherapy and 50% for the atezolizumab + daratumumab combination in the TC2/TC3 subgroup, the lower bound of the 90% CI for the difference in ORR would exclude 0 (ie, a positive signal in favor of the combination).

11.3. Efficacy Analyses

The primary endpoint will be evaluated after approximately 90 subjects have been enrolled. The DMC will perform additional interim analyses after approximately 40 subjects and 60 subjects have had at least 1 disease assessment, respectively. These analyses will include an evaluation of efficacy as a function of PD-L1 expression. Based on these results, the DMC may recommend restricting enrollment of subjects in PD-L1 subgroups in whom clinical benefit is not demonstrated or expanding enrollment by a maximum of 100 subjects in PD-L1 subgroups without adequate enrollment (see Section 11.2) in accordance with the product label of the Ventana SP-142 assay. Study sites will be notified in writing of any changes to enrollment based on DMC recommendations.

Number and percent of subjects in each response category will be tabulated, along with those for subjects who achieve overall response (CR or PR) and who achieve disease control (ie, CBR: CR, PR, or SD with duration of at least 16 weeks). Odds ratio and its 95% confidence interval will be provided as a measure of treatment effect. Descriptive summaries (mean, standard deviation, median, and range) will be provided for time to response among those subjects who have CR or PR.

For time-to-event endpoints (PFS, OS, and duration of response), Kaplan-Meier estimates of the survival functions will be presented. For PFS and OS, Cox's regression will be performed to obtain the hazard ratio estimate and the corresponding 95% CI, which will be used as a measure for treatment effect. Additional Cox's regression may be performed to include appropriate baseline prognostic variables. Furthermore, exploratory analyses for OS may be performed to adjust for the effect of crossover. Analysis of duration of response will be performed descriptively among those subjects who achieve CR or PR.

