3.2. Study Conduct After DMC Recommendations

As of 25 May 2018, the Sponsor terminated further enrollment into this study. Ongoing treatment with daratumumab will be discontinued in all active subjects receiving combination therapy (subjects randomized to the combination Arm B, as well as subjects randomized to Arm A who have crossed over into Arm B). Crossover to Arm B is also no longer permitted. Ongoing subjects will be given the option to continue on atezolizumab monotherapy until the subject meets one or more of the treatment discontinuation criteria in Section 10.2. For subjects remaining on the study, protocol procedures and the atezolizumab dosing schedule will continue according to Section 9.2 and the Time and Events Schedule (Table 1) until locking of the clinical database. All procedures outlined in previous versions of this protocol pertaining to patients randomized to treatment other than atezolizumab monotherapy (in Table 2 through Table 7, which were removed beginning with the implementation of Amendment 6) will no longer be performed. For safety reporting changes, see Section 12.4. Upon clinical database closure, only serious adverse events will be reported and entered in the Sponsor safety repository for subjects who continue to be treated according to local regulatory approval and standard of care guidelines.^{50,51}

The changes to study conduct and status implemented in Amendment 7 were also pursuant to these recommendation from the DMC.

A clinical study report (CSR) will be prepared based on the interim analysis data reviewed by the DMC at the third DMC review (prior to discontinuation of enrollment and daratumumab dosing).

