2.3.3. Response-evaluable Analysis Set

Response-evaluable analysis set includes all randomized subjects who have received at least 1 administration of study medication and have at least 1 adequate post baseline disease assessment. Response related endpoints will also be analyzed based on this analysis set as appropriate.

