5.1.2. Data Handling Rules

There is no imputation planned for missing efficacy endpoint values.

For cross-over subjects, efficacy data after initiation of cross-over treatment may be summarized separately, as applicable.

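### The primary ORR analysis is triggered by enrolment with no minimum follow-up, so ITT subjects whose first scan is not yet due stay in the denominator and cannot be responders

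*Protocol*

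**What the plan says.** Protocol 11.3 sets the timing of the primary analysis: "The primary endpoint will be evaluated after approximately 90 subjects have been enrolled". The next sentence covers the earlier looks: "The DMC will perform additional interim analyses after approximately 40 subjects and 60 subjects have had at least 1 disease assessment, respectively". Protocol 11.9 and SAP 1.2 and 3 describe all three reviews by number enrolled. Neither document gives a minimum follow-up, a number of scans or a data cut-off for primary ORR.

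Protocol Table 1 schedules imaging every 6 weeks (±1 week) for the first 12 months, counted from Cycle 1 Day 1. Protocol 11.1 makes ITT the primary efficacy population, and SAP 2.3.1 defines it as everyone who entered the randomised phase. SAP 5.2 defines ORR as a proportion of subjects and lists not evaluable (NE) among the tabulated categories. On missing data, SAP 5.1.2 says: "There is no imputation planned for missing efficacy endpoint values". ORR is also analysed in the response-evaluable set, whose members must have been treated and must "have at least 1 adequate post baseline disease assessment" (SAP 2.3.3).

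Protocol 3.2 adds that the study report "will be prepared based on the interim analysis data reviewed by the DMC at the third DMC review". Protocol 1.4 dates that review to 23 May 2018, with 88 subjects, 44 per arm. Enrolment was terminated on 25 May 2018.

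**The concern.** The decisive analysis has a weaker maturity rule than the interim looks before it. A subject randomised shortly before the cut has had no chance to show a response, yet ORR over all ITT subjects puts that subject in the denominator and not in the numerator. No sentence calls such a subject a non-responder. That reading follows from the ITT denominator, the absence of imputation and the NE category.

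The report is tied to a cut made two days before enrolment closed, so nothing in the plan guarantees follow-up for the last subjects. If the combination truly raises ORR, equal immaturity in the two arms shrinks the absolute difference and the odds ratio, and the design loses power it was sized to have. Protocol 9.4.2 also notes that responses to immunotherapy can come later than with cytotoxic agents, so even one scan may be too few.

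The second ORR population does not settle the matter. It removes subjects not yet due a scan, but also any who died or deteriorated before a scan, and those are genuine treatment failures.

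**Working it through.** **Inputs from the documents.** ORR is 20% on monotherapy and 40% on the combination; "90 subjects need to be randomized with a 1:1 ratio" to "achieve 80% power to detect this difference with a one-sided alpha of 0.10" (Protocol 11.2). The data cut has 44 per arm (Protocol 1.4). The first scan is at 6 weeks ±1 (Table 1).

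**Input not in the documents.** The share *f* of ITT subjects with no scan at the cut. It is assumed equal in both arms and varied.

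**Step 1: the plan's own figure.** With 45 per arm and one-sided alpha 0.10, power is 79.0% (normal approximation, pooled variance under the null), 79.9% (unpooled) and 80.0% (exact binomial enumeration of the chi-square test). The stated 80% reproduces.

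**Step 2: dilution.** With a share *f* unable to respond, the observed rates are 0.20(1−f) and 0.40(1−f), and the denominators do not change. At f = 0.20, for example, they are 0.20 × 0.80 = 16% and 0.40 × 0.80 = 32%. The odds ratio is (0.32/0.68)/(0.16/0.84) = 2.47, against (0.40/0.60)/(0.20/0.80) = 2.67 with no dilution. The risk ratio stays at 2.0.

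**Step 3: power with 44 per arm** (exact enumeration of the score test, one-sided 0.10).

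| Unscanned share f | Observed ORR | Difference (points) | Odds ratio | Power |
|---|---|---|---|---|
| 0 | 20.0% vs 40.0% | 20.0 | 2.67 | 79.1% |
| 5% | 19.0% vs 38.0% | 19.0 | 2.61 | 76.6% |
| 12% | 17.6% vs 35.2% | 17.6 | 2.54 | 73.2% |
| 18% | 16.4% vs 32.8% | 16.4 | 2.49 | 70.4% |
| 20% | 16.0% vs 32.0% | 16.0 | 2.47 | 69.4% |

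**Step 4: how large might f be?** There is no accrual curve. The only anchors are the closure of TC0 enrolment on 16 January 2018 (Protocol 5), which followed a look at 40 evaluable subjects (Protocol 4), and the 88 subjects reviewed on 23 May 2018, 127 days or 18.1 weeks later. Assume n₀ subjects randomised by 16 January, constant accrual afterwards, and 88 as the total at the cut. Then f = 6 × (88 − n₀)/18.1/88:

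- n₀ = 40: 2.65 per week, 15.9 subjects, f = 18%
- n₀ = 55: 1.82 per week, 10.9 subjects, f = 12%
- n₀ = 65: 1.27 per week, 7.6 subjects, f = 9%, power about 75%

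The first case is probably an upper bound, because more than 40 are likely to have been randomised by the time 40 were evaluable. These figures illustrate the scale and are not estimates of what happened.

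**Step 5: what is left out.** Subjects with one scan who would respond at a later one would lower power further. Unequal immaturity between arms could move the result either way.

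**The case against.** The strongest reply is that the timing language is loose. Protocol 11.9 describes all three reviews by number enrolled, while 11.3 ties the first two to a disease assessment and Protocol 4 reports the first as 40 evaluable subjects. An analysis after 90 are enrolled need not be immediate. Detail is also deferred to a DMC charter and to the data presentation specifications (SAP 2.5), which are not available here. This shows that a mature cut was permitted, but nothing in the protocol or SAP requires one.

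The second reply is that no power figure can be stated as fact. This stands. The unscanned share is not given, eligibility narrowed to TC1-3 after January 2018 so constant accrual is unsupported, and the SAP names no test. The power figures therefore refer to the design calculation only.

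The third is that the effect on the planned measure is small. The odds ratio falls from 2.67 to about 2.5, the risk ratio does not move, and equal immaturity creates no bias if there is no true effect. This also stands, and it limits the size of the point.

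A reader might infer two stronger things. One is that immaturity produced the finding of no observed benefit. The documents do not support this: the DMC reviewed the totality of data and noted more deaths in the combination arm, a signal that does not depend on scans. The other is that the response-evaluable set favours the combination arm by removing its early deaths. The documents report a difference in the number of deaths but no timing, so the size and direction of that effect are unknown.

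**Conclusion.** The concern holds in conditional form. As written, the trigger lets the primary ORR be computed while some ITT subjects have had no opportunity to respond, and neither analysis set handles those subjects cleanly.

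Over an assumed unscanned share of 5% to 20%, equal in both arms, power falls from 79% to between 77% and 69%. A share of 12% to 18%, which needs the accrual assumptions above, gives 73% to 70%. These figures assume true rates of 20% and 40%, 44 per arm and a one-sided test at 0.10. The loss is moderate. The point bears on how the reported ORR is defined and read; it gives no ground for revisiting the decision to stop.

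**What to change.** 1. **Cut-off.** In Protocol 11.3 and SAP 5.2, set the primary ORR data cut so that every randomised subject has had the opportunity for a minimum number of scheduled scans, or has died, progressed or left the study. The minimum should be at least the first scan (6 + 1 = 7 weeks) and preferably the second (12 + 1 = 13 weeks).
2. **NE.** State in SAP 5.2 that NE counts as non-response in the ITT analysis.
3. **Response-evaluable set.** In SAP 2.3.3, exclude only subjects whose first scan is not yet due. Count death or clinical progression before the first scan as non-response.
4. **If the report stays on the 23 May 2018 data.** Give the number per arm with no scan yet due, and add an ORR analysis limited to subjects randomised at least 7 (or 13) weeks before the cut.

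Items 2 to 4 need only text and programming. Item 1 costs a delay of about 7 to 13 weeks after the last randomisation, and there are data limits. Some Arm B scans would fall after daratumumab was stopped. Protocol 9.4 lets assessments end for subjects who stop treatment without progression, whereas 9.1.5 says they must continue; the two need to be reconciled. Protocol 17.8 limits monitoring after Amendment 6 to serious adverse events, so some later scans may be missing or unmonitored. Amendment 7 describes the database as already locked, so a later cut depends on what was collected before lock. If that is insufficient, item 4 is the practical remedy.

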11.4. Pharmacokinetic Analyses

Pharmacokinetic analyses will be performed on the PK-evaluable population, defined as subjects who have received at least 1 dose of daratumumab or atezolizumab and have at least 1 postinfusion sample.

All concentrations below the lowest quantifiable concentration or missing data will be labeled as such in the concentration database. Concentrations below the lowest quantifiable concentration will be treated as zero in the summary statistics. The number of subjects and samples excluded from the analysis will be clearly documented.

Descriptive statistics will be used to summarize daratumumab and atezolizumab serum concentrations at each sampling time point. C_{\min} is defined as the minimal concentration observed immediately before infusion and C_{\max} is defined as the maximum concentration observed at the end of infusion, as presented in the summary of serum concentration by sampling time point and route of administration. Other PK parameters, if available, may also be summarized.

If sufficient data are available, population-PK analysis of serum concentration-time data of daratumumab or atezolizumab may be performed and may be combined with data from other studies. If the population-PK analysis is conducted, details will be given in a population-PK analysis plan and the results of the analysis will be presented in a separate report.

11.5. Immunogenicity Analyses

The incidence of anti-atezolizumab and daratumumab antibodies will be summarized for all subjects who receive at least 1 dose of atezolizumab and daratumumab and have appropriate samples for detection of antibodies to atezolizumab and daratumumab (ie, subjects with at least 1 sample obtained after their first dose). In addition, subjects who are positive for antibodies to atezolizumab or daratumumab will be listed.

Other immunogenicity analyses may be performed to further characterize the immune responses that are generated.

11.7. Pharmacokinetic/Pharmacodynamic Analyses

If sufficient data are available, then other PK/pharmacodynamic modeling may be performed, including exploring the relationship between serum concentrations of atezolizumab and daratumumab and endpoints of clinical efficacy and safety. If performed, details and results of the analysis will be presented in a separate report.

11.8. Safety Analyses

Adverse Events

The verbatim terms used in the CRF by investigators to identify adverse events will be coded using the Medical Dictionary for Regulatory Activities (MedDRA). Treatment-emergent adverse events are AEs with onset during the treatment phase or that are a consequence of a pre-existing condition that has worsened since baseline. All reported adverse events will be included in the analysis. For each adverse event, the percentage of subjects who experience at least 1 occurrence of the given event will be summarized by treatment group. In addition, comparisons between treatment groups will be provided if appropriate.

Summaries, listings, datasets, or subject narratives may be provided, as appropriate, for those subjects who die, who discontinue treatment due to an adverse event, or who experience a severe or a serious adverse event.

Clinical Laboratory Tests

Laboratory data will be summarized by type of laboratory test. Reference ranges and markedly abnormal results (specified in the Statistical Analysis Plan) will be used in the summary of laboratory data. Descriptive statistics will be calculated for each laboratory analyte at baseline and for observed values and changes from baseline at each scheduled timepoint. Changes from baseline results will be presented in pre- versus posttreatment cross-tabulations (with classes for below, within, and above normal ranges). A listing of subjects with any laboratory results outside the reference ranges will be provided. A listing of subjects with any markedly abnormal laboratory results will also be provided.

Parameters with predefined NCI-CTCAE toxicity grades will be summarized. Change from baseline to the worst adverse event grade experienced by the subject during the study will be provided as shift tables.

Electrocardiogram

Electrocardiogram data will be summarized based on categories of normal, abnormal either clinically significant or not clinically significant and listed.

Vital Signs

Descriptive statistics of temperature, pulse/heart rate, and blood pressure (systolic and diastolic) values and changes from baseline will be summarized at each scheduled timepoint. The percentage of subjects with values beyond clinically important limits will be summarized.

11.9. Data Monitoring Committee

An internal Janssen DMC, independent of the study team, will be established to review the efficacy and safety data in the randomization phase. The DMC will consist of a minimum of 3 members with at least 1 clinician and a statistician, 1 of whom will chair the committee. The DMC will review the totality of data after approximately 40, 60, and 90 subjects have been enrolled, and will formulate recommendations on study conduct, including but not limited to future subject enrollment (see Section 11.3). The DMC may request additional ad-hoc reviews as data accumulate to monitor safety or efficacy in certain PD-L1 subgroups. Additional details will be specified in a separate DMC charter.

12. ADVERSE EVENT REPORTING

Timely, accurate, and complete reporting and analysis of safety information from clinical studies are crucial for the protection of subjects, investigators, and the Sponsor, and are mandated by regulatory agencies worldwide. The Sponsor has established Standard Operating Procedures in conformity with regulatory requirements worldwide to ensure appropriate reporting of safety information; all clinical studies conducted by the Sponsor or its affiliates will be conducted in accordance with those procedures.

Method of Detecting Adverse Events and Serious Adverse Events

Care will be taken not to introduce bias when detecting adverse events or serious adverse events. Open-ended and nonleading verbal questioning of the subject is the preferred method to inquire about adverse event occurrence.

12.1. Definitions

12.1.1. Adverse Event Definitions and Classifications

Adverse Event

An adverse event is any untoward medical occurrence in a clinical study subject administered a medicinal (investigational or non-investigational) product. An adverse event does not necessarily have a causal relationship with the treatment. An adverse event can therefore be any unfavorable and unintended sign (including an abnormal finding), symptom, or disease temporally associated with the use of a medicinal (investigational or non-investigational) product, whether or not related to that medicinal (investigational or non-investigational) product. (Definition per International Conference on Harmonisation [ICH]).

This includes any occurrence that is new in onset or aggravated in severity or frequency from the baseline condition, or abnormal results of diagnostic procedures, including laboratory test abnormalities.

Note: The Sponsor collects adverse events starting with the signing of the ICF (refer to Section 12.3.1, All Adverse Events, for time of last adverse event recording).

Serious Adverse Event

A serious adverse event based on ICH and EU Guidelines on Pharmacovigilance for Medicinal Products for Human Use is any untoward medical occurrence that at any dose:

- Results in death
- Is life-threatening
(The subject was at risk of death at the time of the event. It does not refer to an event that hypothetically might have caused death if it were more severe.)
- Requires inpatient hospitalization or prolongation of existing hospitalization
- Results in persistent or significant disability/incapacity
- Is a congenital anomaly/birth defect
- Is a suspected transmission of any infectious agent via a medicinal product
- Is Medically Important.*

*Medical and scientific judgment should be exercised in deciding whether expedited reporting is also appropriate in other situations, such as important medical events that may not be immediately life threatening or result in death or hospitalization but may jeopardize the subject

or may require intervention to prevent one of the other outcomes listed in the definition above. These should usually be considered serious.

If a serious and unexpected adverse event occurs for which there is evidence suggesting a causal relationship between the study drug and the event (eg, death from anaphylaxis), the event must be reported as a serious and unexpected suspected adverse reaction even if it is a component of the study endpoint (eg, all-cause mortality).

Unlisted (Unexpected) Adverse Event/Reference Safety Information

An adverse event is considered unlisted if the nature or severity is not consistent with the applicable product reference safety information. For atezolizumab and daratumumab, the expectedness of an adverse event will be determined by whether or not it is listed within the Reference Safety Information in the Investigator's Brochures.

Adverse Event Associated With the Use of the Drug

An adverse event is considered associated with the use of the drug if the attribution is possible, probable, or very likely by the definitions listed in Section 12.1.2, Attribution Definitions.

12.1.2. Attribution Definitions

Not Related

An adverse event that is not related to the use of the drug.

Doubtful

An adverse event for which an alternative explanation is more likely, eg, concomitant drug(s), concomitant disease(s), or the relationship in time suggests that a causal relationship is unlikely.

Possible

An adverse event that might be due to the use of the drug. An alternative explanation, eg, concomitant drug(s), concomitant disease(s), is inconclusive. The relationship in time is reasonable; therefore, the causal relationship cannot be excluded.

Probable

An adverse event that might be due to the use of the drug. The relationship in time is suggestive (eg, confirmed by dechallenge). An alternative explanation is less likely, eg, concomitant drug(s), concomitant disease(s).

Very Likely

An adverse event that is listed as a possible adverse reaction and cannot be reasonably explained by an alternative explanation, eg, concomitant drug(s), concomitant disease(s). The relationship in time is very suggestive (eg, it is confirmed by dechallenge and rechallenge).

